## 10.5.5. Primary Efficacy Analysis

The primary efficacy endpoint will be analyzed on the

comparing the treatment group to placebo with the randomization strata, Baseline Schirmer's Test Score as the covariate and Mackie Classification Stage as an independent variable. The primary endpoint will be the mean change from baseline in corneal fluorescein staining at Week 8. The analysis using the PP population will be treated as the primary analysis.

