# 5.4. Exclusion Criteria

#### Subjects must not:

- 1. Have Stage 2 or Stage 3 NK affecting one or both eyes.
- 2. Have ocular graft versus host disease or Stevens-Johnson syndrome.
- 3. Have any active ocular infection (COVID-19 conjunctivitis, bacterial, viral, fungal, or protozoal) or active ocular inflammation not related to NK in the affected eye.

- 6. Be currently receiving autologous serum tears, amniotic membrane, cenegermin, Fresh Frozen plasma or cord blood derived tears.
- 7. Have severe blepharitis and/or severe meibomian gland disease in the study eye.

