# **10.2.** Analysis Populations

## 10.2.2. Per Protocol

The per-protocol (PP) population will include all ITT subjects with baseline corneal fluorescein staining  $\geq 2$  in subjects with Stage I (corneal epithelial hyperplasia/punctate keratopathy) NK in one or both eyes. Analysis using the PP population will group subjects according to the treatment to which they were randomized.

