# **10.4.** Sample Size and Power Considerations

# **10.5.** Statistical Analysis

This section briefly outlines the planned efficacy analyses. The statistical analysis plan (SAP) describes the methods to be used in detail. If the SAP and the protocol disagree, the details and methods of the SAP will prevail.

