## 10.5.6. Secondary Efficacy Analysis

The secondary efficacy endpoints are as follows:

• Mean change from baseline in visual acuity at Week 8

The secondary efficacy endpoint will be analyzed on the PP population using an analysis of covariance model comparing the treatment group to placebo with randomization strata, baseline Schirmer's Test Score and the baseline ETDRS visual acuity as covariates.

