#### 2 Introduction

This statistical analysis plan (SAP), which is based on the final protocol (Amendment 6) of the study protocol dated June 15, 2022, defines the methods, and analyses that Oyster Point Pharma, Inc. (henceforth, Oyster Point) plans to use to analyze the data from Protocol OPP-102. This SAP complies with guidance promulgated by the International Conference on Harmonization (ICH) and the US Food and Drug Administration (FDA). If the protocol is subsequently amended, this SAP may be amended as well. Should the SAP and the protocolbe inconsistent with respect to the planned analyses, the language of the SAP prevails.

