# 14.1 Primary Efficacy Endpoints

[figure not shown]

[figure not shown]
The primary endpoint will be the mean change from baseline in cornstaining at Week 8. The primary efficacy endpoint will be analyzed on the PP population using an analysis of covariance model comparing the treatment group to placebo with the randomization strata, baseline Schirmer's Test Score and the baseline corneal fluorescein staining as the covariates.

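### Do the differing covariate lists in protocol 10.5.5 and SAP 14.1 leave the primary model unsettled?

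*Protocol*

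**What the plan says.** Both documents have the same primary outcome (Week 8 change in corneal staining) and the same primary population (per-protocol). Both adjust for the randomization strata and the baseline Schirmer's score. They part on the remaining term.

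- Protocol 10.5.5: "Baseline Schirmer's Test Score as the covariate and Mackie Classification Stage as an independent variable".
- SAP 14.1: "baseline Schirmer's Test Score and the baseline corneal fluorescein staining as the covariates".

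On authority, protocol 10.5 presents itself as a brief outline and states "If the SAP and the protocol disagree, the details and methods of the SAP will prevail". SAP section 2 says that where the two are inconsistent "with respect to the planned analyses, the language of the SAP prevails".

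On stage at entry, exclusion 1 in protocol 5.4 reads "Have Stage 2 or Stage 3 NK affecting one or both eyes", inclusion 2 requires Stage 1, and protocol 10.2.2 builds the per-protocol set from baseline staining of at least 2 "in subjects with Stage I (corneal epithelial hyperplasia/punctate keratopathy) NK in one or both eyes".

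For comparison, the secondary model in protocol 10.5.6 uses the strata, "baseline Schirmer's Test Score and the baseline ETDRS visual acuity as covariates", so it does adjust for the baseline of its own outcome.

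**The concern.** A reader who compares the two sections finds one covariate removed and another added in the primary model, which is the one place where a plan should leave no choice. Whether the baseline value of the outcome is in the model affects precision. If an analyst could pick between the two models after seeing the data, the nominal 5% level would no longer hold.

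The Mackie term is also odd in itself. The protocol does not say which stage value is meant. At entry everyone is Stage 1. The visit lists in protocol 8.3.1 show staging at Visits 2 to 6 and at early termination, but not at Visit 1. The term is therefore either constant or measured after randomization.

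Finally, the SAP describes itself as a plan "which is based on the final protocol (Amendment 6) of the study protocol dated June 15, 2022", while the page line of the protocol supplied reads 10 Nov 2022. That raises the question of whether the Mackie wording is a later change that the SAP never took in.

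**Working it through.** **1. The two lists side by side**

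| Term | Protocol 10.5.5 (visible text) | SAP 14.1 |
|---|---|---|
| Treatment | yes | yes |
| Randomization strata | yes | yes |
| Baseline Schirmer's score | yes | yes |
| Baseline corneal staining | not listed | yes |
| Mackie stage | yes | no |

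The protocol sentence has a gap before its covariate list, so the absence of baseline staining is established only for the text that can be read. The Mackie term differs either way.

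**2. Which list is run.** Each document names the SAP as controlling when they disagree. SAP 14.1 is a complete specification: population, model and covariates. Following the plan as written gives exactly one primary analysis.

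**3. What the omitted stage term could have contributed.**

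- *Read as baseline stage.* It has one level. A design with intercept, treatment, stratum, Schirmer's score and stage has five columns and rank 4, because the stage column duplicates the intercept. In 500 simulated trials of 100 subjects, fits with and without that column gave treatment estimates and standard errors agreeing to within 1e-13, as the algebra requires.
- *Read as recorded staging.* Visits 2 to 6 follow randomization, and treatment may affect stage. Adjusting for it would change the effect being estimated and could bias it.

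Neither reading is a reason to carry the term into the SAP.

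**4. What the protocol list would cost if it were run instead.** There is no power figure to reproduce: protocol 10.4 and SAP section 6 show no text beyond their headings. Let k be baseline SD divided by Week 8 SD, and ρ the correlation between baseline and Week 8. The variance of the treatment effect without baseline staining, relative to the variance with it, is

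R = (k² + 1 − 2ρk) / (1 − ρ²) = 1 + (k − ρ)² / (1 − ρ²).

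If the SAP model had 80% power, power without baseline staining would be Φ(2.802/√R − 1.960). The documents give neither k nor ρ, so these values are assumed:

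| k | ρ | R | Power |
|---|---|---|---|
| 0.6 | 0.5 | 0.76/0.75 = 1.01 | 80% |
| 1.0 | 0.7 | 0.60/0.51 = 1.18 | 73% |
| 1.0 | 0.5 | 1.00/0.75 = 1.33 | 68% |
| 1.0 | 0.3 | 1.40/0.91 = 1.54 | 62% |
| 1.25 | 0.3 | 1.8125/0.91 = 1.99 | 51% |

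The penalty runs from almost nothing to a doubling of the variance, depending on inputs nobody can read from the plan. No single figure can be defended.

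**5. Error rate.** In 20,000 simulated null trials at each assumed ρ (50 per arm, Gaussian outcome, k = 1, ρ from 0.3 to 0.7), each model alone rejected in 4.7% to 4.9%. Reporting whichever was significant rejected in 6.5% to 7.4%. That excess needs a free choice between models, which step 2 removes.

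**The case for a change.** The best case for acting is that this is more than wording. The two texts specify different models, and under the assumptions above they can disagree on significance. In simulation at an effect giving the SAP model 80% power, with k = 1, they disagreed in 23%, 17% and 12% of trials for ρ of 0.3, 0.5 and 0.7. A precedence clause says which text applies but not which was intended. If the November 2022 protocol postdates the SAP, the Mackie term might be a deliberate revision. Correcting one sentence before unmasking would cost almost nothing.

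Part of this stands. The models are different, and someone checking a report against protocol 10.5.5 would need the precedence clause to explain what they see.

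The rest does not carry. The protocol bearing the later date itself retains the clause handing authority to the SAP, so the order of versions does not alter which model governs. The version question cannot be settled here: the front pages are removed, the SAP's revision entries are not visible, and SAP section 2 allows for later protocol amendments. A page date supports a check of the reference, not a finding of error. The disagreement rates and the 6.5% to 7.4% error rate describe a trial in which either model might be reported, which the plan excludes.

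Nor can it be said that restricting the per-protocol set to baseline staining of at least 2 makes the gap larger. In the same linear setting, R − 1 equals (1 − b)² times baseline variance over residual variance, where b is the slope of Week 8 on baseline. Selection on baseline leaves b and the residual variance alone and shrinks the baseline variance. With ρ = 0.5 and k = 1, b is 0.5 and the residual variance 0.75. Cutting the baseline SD to 60% gives R = 1 + 0.25 × 0.36/0.75 = 1.12, down from 1.33.

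**Conclusion.** No change to the plan follows. The discrepancy is real in the visible text but clerical in effect. One complete primary model stands in SAP 14.1, both documents make it the controlling one, and it includes the covariate that matters for precision. The effect on the primary result is nil. Editing the protocol sentence would alter neither what is analyzed nor what is concluded; it would only spare a reader from having to find the precedence clause.

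This rests on one condition, that the analysts follow the precedence rule stated in protocol 10.5 and SAP section 2. It does not depend on the assumed k and ρ, on which reading of Mackie stage was meant, or on which protocol version the SAP was written against.

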## 10.5.6. Secondary Efficacy Analysis

The secondary efficacy endpoints are as follows:

• Mean change from baseline in visual acuity at Week 8

The secondary efficacy endpoint will be analyzed on the PP population using an analysis of covariance model comparing the treatment group to placebo with randomization strata, baseline Schirmer's Test Score and the baseline ETDRS visual acuity as covariates.

# 10.5.7. Safety Analysis

All safety analyses will be performed on the safety population.

The safety of OC-01 (varenicline) will be assessed primarily by the incidence of AEs. An AE will be considered a treatment-emergent AE (TEAE) if it occurs or worsens on or after initiation of treatment. An overall summary of TEAEs will be presented including the number of events and the number of subjects with events (along with percentages) by treatment group for TEAEs in several categories base on seriousness, relationship to treatment, and severity.

Other safety endpoints including visual acuity, slit lamp bio microscopy and intranasal examination will be summarized by treatment group and visit using descriptive statistics. Changes or shifts from baseline will be summarized where appropriate. For assessments performed by eye, study eye and fellow eye will be summarized separately.

The SAP will present methods of analysis of these defined parameters in detail.

## 10.5.8. Interim Analysis

No interim analysis is planned for this study.

# 11. COMPLIANCE WITH GOOD CLINICAL PRACTICES, ETHICAL CONSIDERATIONS, AND ADMINISTRATIVE ISSUES

This study will be conducted in compliance with this protocol, Good Clinical Practices, including the International Conference on Harmonization (ICH) Guidelines, and in general, consistent with the Declaration of Helsinki. In addition, all applicable local, state, and federal requirements relevant to the use of study drugs in the countries involved will be adhered to.

# 11.1. Protection of Human Subjects

## 11.1.1. Subject Informed Consent

Informed consent/assent must take place before any study specific procedures are initiated. Signed and dated written informed consent must be obtained from each subject and/or from the subject's parent or legal guardian prior to enrollment into the study. If the subject is under the legal age of consent, the consent form must be signed by a legal guardian or as required by state and/or local laws and regulations.

All informed consent/assent forms must be approved for use by the Sponsor and receive approval/favorable opinion from an IRB prior to their use. If the consent form requires revision (e.g., due to a protocol amendment or significant new safety information), it is the Investigator's responsibility to ensure that the amended informed consent is reviewed and approved by Sponsor prior to submission to the governing IRB and that it is read, signed and

dated by all subjects subsequently enrolled in the study as well as those currently enrolled in the study.

If informed consent is taken under special circumstances (oral informed consent), then the procedures to be followed must be determined by Sponsor and provided in writing by Sponsor prior to the consent process.

#### 11.1.2. **Institutional Review Board Approval**

This study is to be conducted in accordance with IRB regulations [U.S. 21 Code of Federal regulations (CFR) Part 56.103]. The Investigator must obtain appropriate IRB approval before initiating the study and re-approval at least annually.

Only an IRB-approved version of the informed consent form will be used.

#### 11.2. **Ethical Conduct of Study**

This study will be conducted in accordance with the ethical principles that originated with the Declaration of Helsinki.

#### 11.3. **Subject Confidentiality**

All personal study subject data collected and processed for the purposes of this study should be maintained by the Investigator and his/her staff with adequate precautions so as to ensure the confidentiality of the data in accordance with local, state, and federal laws and regulations.

Monitors, auditors and other authorized representatives of the Sponsor, the IRB approving this study, the Food and Drug Administration, the Department of Health and Human Services, other domestic government agencies, and other foreign regulatory agencies will be granted direct access to the study subject's original medical and study records for verification of the data and/or clinical trial procedures. Access to this information will be permitted to the above listed individuals to the extent permitted by law.

A report of the results of this study may be published or sent to the appropriate health authorities in any country in which the study drug may ultimately be marketed, but the subject's identity will not be disclosed in these documents.

#### 11.4. **Documentation**

Source documents may include a subject's medical records, hospital charts, clinic charts, the Investigator's study subject files, as well as the results of diagnostic tests such as photographs, X-rays, laboratory tests, and electrocardiograms. The Investigator's copy of the CRFs serves as the Investigator's record of a subject's study-related data.

#### 11.4.1. **Retention of Documentation**

All study related correspondence, subject records, consent forms, record of the distribution and use of all study drug and copies of CRFs should be maintained on file for at least two years after the last approval of a marketing application in an ICH region and until there are no pending or contemplated marketing applications in an ICH region; or until at least two years have elapsed since the formal discontinuation of clinical development of the study drug. These Confidential

documents will be retained for a longer period if required by the applicable regulatory requirements or by an agreement with the Sponsor. It is the responsibility of the Sponsor to inform the Investigator/institution as to when these documents no longer need to be retained.

If the responsible Investigator retires, relocates, or for other reasons withdraws from the responsibility of keeping study records, custody must be transferred to a person who will accept the responsibility. The Sponsor must be notified in writing of the name and address of the new custodian.

# 11.5. Labeling, Packaging, Storage, Accountability, and Return or Disposal of Study Drug

# 11.5.1. Labeling/Packaging

The study drug/placebo nasal spray will be provided in multi-use intranasal applicator that will be assigned at randomization for use during study.

# 11.5.2. Storage of Study Drug/Placebo Nasal Spray

The study drug/placebo nasal spray must be stored in accordance with the pharmacy manual for this study, which contains detailed information regarding the storage and administration.

# 11.5.3. Accountability of Study Drug

The study drug/placebo nasal spray is only prescribed by the principal Investigator or his/her named sub investigator(s) and is to only be used in accordance with this protocol. The study drugs must only be distributed to subjects properly qualified under this protocol to receive study drug. The Investigator must keep an accurate accounting of the study drugs by maintaining a detailed inventory. This includes the amount of study drugs received by the site, amount dispensed to subjects, amount returned to the site by the subjects, and the amount returned to the Sponsor upon the completion of the study.

## 11.5.4. Return or Disposal of Study Drug

You may be requested to destroy study drug or study drug kits on-site that are expired, not acceptable for use due to a temperature deviation, or at the end of the study. If site regulations do not permit destruction, study drugs will be returned to the Sponsor or their designee for destruction.

# 11.6. Recording of Data on Source Documents and Electronic Case Reports Forms

All subject data will be captured in the subject source documents which will be transcribed in the eCRFs. The Investigator is responsible for ensuring that study data is completely and accurately recorded on each subject's eCRF, source documents, and all study-related materials. All study data should also be attributable, legible, contemporaneous, and original. A recorded datum should only be corrected in a manner that does not obliterate, destroy, or render illegible the previous entry (e.g., by drawing a single line through the incorrect entry and writing the revision next to the corrected data). An individual who has corrected a data entry should make

clear who made the correction and when, by adding to the correction his/her initials as well as the date of the correction.

Data entry of all enrolled and randomized subjects will use software that conforms to 21 CFR Part 11 requirements and will be performed only by staff who have been trained on the system and have access to the system. Minimal data will be entered for screen failure subjects. An audit trail will be maintained within the electronic system to capture all changes made within the eCRF database. After the end of the study and database lock, electronic copies of all applicable subjects' eCRFs will be provided to each Investigator Site to be maintained on file by the Investigator.

[figure not shown]
# 11.7. Handling of Biological Specimens

Not applicable.

## 11.8. Publications

The study will be documented in a final report, which will contain appropriate statistical analysis and medical overview. No individual site or Investigator may publish or present any results from the study until the Sponsor completes a joint, multi-center publication of the trial results in conjunction with various participating Investigators and appropriate sites contributing data and comments. Subsequently, individual Investigators may request to publish or present results from the trial; however, approval will be at the sole discretion of the Sponsor. Should the foregoing language conflict with the language addressing publication in the clinical trial agreement, the language in the Clinical Trial Agreement will prevail.

# 13. APPENDICES

Sponsor: Oyster Point Pharma, Inc. 10 Nov2022

# APPENDIX 2: EXAMINATION PROCEDURES, TESTS, EQUIPMENT, AND TECHNIQUES

The following examination procedures, tests, equipment, and techniques are listed in this Appendix:

Stage	Clinical Findings		
Ι	Corneal epithelial hyperplasia and irregularity		
	Scattered small facets of dried epithelium (Gaule spots)		
	Superficial punctate keratopathy		
	Rose bengal staining of inferior conjunctiva		
	Increased viscosity of tear mucus		
	Decreased breakup time		
	Superficial neovascularization Stromal Scarring		
	Dellen		
II	Persistent corneal epithelial defect with smooth and rolled edges		
	Descemet's membrane folds and stromal swelling		
	Anterior chamber inflammatory reaction with hypopyon (rare)		
III	Corneal ulcer		
	Corneal perforation		
	Corneal stromal melting		

#### Table 1: Clinical Grading of Neurotrophic Keratopathy

# GUIDELINES FOR MEASURING VISUAL ACUITY TO THE STANDARD PROCEDURE DEVELOPED FOR THE EARLY TREATMENT DIABETIC RETINOPATHY STUDY (ETDRS)

# **Visual Acuity Equipment and Facilities:**

The procedure described in this section utilizes the following equipment:

- Set of three ETDRS Distance Visual Acuity Test charts which are modified ETDRS Charts 1, 2 and R for testing visual acuity at 4 meters
- Retro-illuminated box providing standardized chart illumination

Visual acuity testing is required at a distance of 4 meters and, for subjects with sufficiently reduced vision, at 1 meter. The 4-meter distance should be marked clearly and permanently. The 1-meter distance must be measured with a 1-meter stick when the subject is seated (see below)

# **Visual Acuity Charts**

Charts 1 and 2 are used for testing the right and left eye, respectively, and Chart R is used for entering acuity measurements and refraction for each eye. The features of the charts are high contrast Sloan Letters in each of 14 lines, lines of equal difficulty, and a geometric progression of letter size (and, thus, an arithmetic progression of the logarithm of minimum angle of resolution) from line to line. Charts 1, 2, and R have different letter sequences. Subjects should be prevented from seeing Charts 1 and 2 until refraction has been completed and the visual acuity test begins.

## **Visual Acuity Box**

The dimensions of the light box are 24 /4 inches by 7 inches. The box can be mounted on a wall or on a cylindrical stand. The stand is mounted on a five-pronged wheelbase, with each prong about 14 inches long; two of the five wheels are lockable. When the box is mounted on the stand, its height can be varied.

The light box should be mounted at a height such that the top of the third row of letters (0.8 log MAR) is 49 (2 inches  $\pm$ ) from the floor. The rear of the box provides storage space for the two charts not being used.

